2.4 Derivation of Response Status and Non-Responder Imputation

For each 'complete' dataset, the imputed post-baseline values will be rounded to the same precision as the observed data. Response status (e.g., EASI 75 at each visit) will be determined accordingly.

The imputed response status for missing due to reasons other than COVID-19 will be overridden by non-responder imputation (Section 2.1) to ensure that multiple imputation is only applied to missing due to COVID-19:

- Using NRI approach, all missing due to reasons other than COVID-19 will be categorized as non-responders, including visits after a subject receives rescue medication. In addition, subjects whose change/percent change from Baseline cannot be calculated because of a missing Baseline will be considered as a non-responder at all post-baseline visits.
- The only exception is that a subject will be categorized as a responder for the visit if the subject is a responder both before and after an SAP-specified visit window.

2.5 Analysis

The statistical analysis will use the Cochran-Mantel-Haenszel (CMH) test adjusted by the stratification factors.

2.5.1 Analysis of Each Dataset

For each of the K 'complete' datasets, the CMH test will be used to estimate the treatment difference versus placebo and the corresponding standard error.

2.5.2 Synthesis of Results for Statistical Inference

The results from the K 'complete' datasets will be synthesized using the SAS procedure PROC MIANALYZE, following Rubin's formula (Rubin, 1987³), to derive the MI estimator of the treatment difference for the final inferences.

Rubin's formula

We fit the analysis model to the k^{th} 'complete' dataset, denoting the estimate of the treatment difference q by $\tilde{\theta}_k$ from the k^{th} 'complete' dataset, and denoting the corresponding estimate of the variance as V_k .

The MI estimator of q (point estimator obtained from PROC MIANALYZE), $\tilde{\theta}_{MI}$, is the average of the K individual estimators:

$$\tilde{\theta}_{MI} = \frac{1}{K} \sum_{k=1}^K \tilde{\theta}_k.$$

The estimated variance of $\tilde{\theta}_{MI}$, is a combination of the between- and within-imputation variability as follows:

$$V_{MI} = W + (1 + \frac{1}{K})B,$$

where $W = \frac{1}{K} \sum_{k=1}^K V_k$ is the within-imputation variability and $B = \frac{1}{K-1} \sum_{k=1}^K (\tilde{\theta}_k - \tilde{\theta}_{MI})^2$

is the between-imputation variance.

It has been shown¹ that the statistic

$$T = \frac{\tilde{\theta}_{MI} - \theta}{\sqrt{V_{MI}}}$$

has an approximate t_v distribution where $v = (K - 1)(1 + \frac{W}{B})^2$. Statistical inference, including hypothesis testing and confidence intervals for the treatment effect, will be based on this T-statistic.

3.0 Sample SAS Code

```
/*IMPUTATION STEP – DETERMINE IMPUTATION DISTRIBUTION AND RANDOMLY
IMPUTE MISSING VALUE TO GENERATE 'COMPLETE' DATASETS*/
/*****************/
PROC MI DATA=EASI_MONO OUT=EASI_FULL NIMPUTE=1 SEED= 22040 /*RANDOM
SEED PRE-DEFINED*/
    ROUND=. . . 0 1 0 1 0 1 0 1 0 1 0 1 0 1 0 1 0 1 0 1 /*VALUE ROUND TO 1ST
DECIMAL*/
    MIN=. . . 0 0 0 0 0 0 0 0 0 0 0 0 0 0 0 0 0 0 0 0 0 0 /*MINIMUM VALUE OF EASI IS
0*/
    MAX=. . . 72 72 72 72 72 72 72 72 72 72 72 72 72 72 72 72 72 72 72 72 72 72 /*MAXIMUM VALUE OF EASI IS
72*/
    MINMAXITER=1000;
    CLASS TRT01PN VIGAN SEXN;
    VAR TRT01PN VIGAN SEXN BASE WK1 WK2 WK4 WK8 WK12 WK16 WK20 WK24;
    MONOTONE REG (WK1 WK2 WK4 WK8 WK12 WK16 WK20 WK24); /* IMPUTED
SEQUENTIALLY, FROM WK 1 TO 24, WITH COVARIATES CONSTRUCTED FROM THE
CORRESPONDING PRECEDING VARIABLES*/
    BY _IMPUTATION_; /*FOR EACH OF THE 30 MONOTONE
MISSING DATASETS, IMPUTE A 'COMPLETE' DATASET*/
RUN;

/*DETERMINE DICHOTOMOUS RESPONSE STATUS, EASI 75*/
DATA ALL; SET EASI_FULL;
    IF 0<=WK1<=0.25*BASE THEN EASI75_1=1;
    ELSE EASI75_1=0;
    IF 0<=WK2<=0.25*BASE THEN EASI75_2=1;
    ELSE EASI75_2=0;
    IF 0<=WK4<=0.25*BASE THEN EASI75_4=1;
    ELSE EASI75_4=0;
    IF 0<=WK8<=0.25*BASE THEN EASI75_8=1;
    ELSE EASI75_8=0;
    IF 0<=WK12<=0.25*BASE THEN EASI75_12=1;
    ELSE EASI75_12=0;
    IF 0<=WK16<=0.25*BASE THEN EASI75_16=1;
    ELSE EASI75_16=0;
    IF 0<=WK20<=0.25*BASE THEN EASI75_20=1;
    ELSE EASI75_20=0;
    IF 0<=WK24<=0.25*BASE THEN EASI75_24=1;
    ELSE EASI75_24=0;

RUN;

/*****************/
/*
/*          DATA HANDLING STEPS TO MERGE COVID-19 STATUS OMITTED
*/
```

```

/*
   PLACE TO ADD DATA HANDLING AND MERGING STEPS
*/
*****

/*FOR MI, SKIP THE FOLLOWING CODE, PROCEED TO THE CODE AFTER ANALYSIS
MODEL *//*OVERRIDE MISSING VALUES NOT DUE TO COVID-19 WITH TRADITIONAL
NRI*/
DATA ALLF; SET ALL;
  /*COVID19_XX='Y' IF MISSING AT WEEK XX IS DUE TO COVID-19; IF NOT,
OVERRIDE WITH TRADITIONAL NRI*/
  IF COVID19_1 NE 'Y' THEN EASI75_1=EASI75NRI_1;
  IF COVID19_2 NE 'Y' THEN EASI75_2=EASI75NRI_2;
  IF COVID19_4 NE 'Y' THEN EASI75_4=EASI75NRI_4;
  /*VARIABLE EASI75NRI XX: TRADITIONAL NRI DATA AT WEEK XX, WHICH COVERS
THE SPECIAL HANDLING SUCH AS THE BEFORE-AND-AFTER EXCEPTION*/
  IF COVID19_8 NE 'Y' THEN EASI75_8=EASI75NRI_8;
  IF COVID19_12 NE 'Y' THEN EASI75_12=EASI75NRI_12;
  IF COVID19_16 NE 'Y' THEN EASI75_16=EASI75NRI_16;
  IF COVID19_20 NE 'Y' THEN EASI75_20=EASI75NRI_20;
  IF COVID19_24 NE 'Y' THEN EASI75_24=EASI75NRI_24;
RUN;
PROC SORT DATA=ALLF; BY _IMPUTATION_ SUBJID; RUN;

*****/
/*ANALYSIS MODEL*/
*****

/*KEY CODE: ANALYZING EACH 'COMPLETE' DATASET*/
*****/
/*COMPARE TREATMENT GROUPS 1 (DUPILUMAB) AND 2 (UPADACITINIB) */

/*INDIVIDUAL-LEVEL DATA --> # OF RESPONDERS & # OF SUBJECTS, TO BE READ-
IN TO PROC STDRATE*/
PROC FREQ DATA=ALL;
  BY _IMPUTATION_;
  TABLES TRT01PN*STRATAN*EASI75_16/LIST NOCUM NOPRINT OUT=COUNT_TABLE;
  /*WEEK 16 RESULTS AS AN EXAMPLE*/
RUN;
DATA COUNT_TABLE; SET COUNT_TABLE;
  DROP PERCENT;
RUN;
PROC TRANSPOSE DATA=COUNT_TABLE OUT=FREQ_TABLE PREFIX=RESP;
ID EASI75_16;
BY _IMPUTATION_ TRT01PN STRATAN;
VAR COUNT;
RUN;
DATA FREQ_TABLE1; SET FREQ_TABLE;
  CASE=RESP1;

```

```
SIZE=SUM(RESP0, RESP1);  
KEEP _IMPUTATION_ TRT01PN STRATAN CASE SIZE;  
RUN;  
  
/*RE-ORDER TO SET 1 (PLACEBO) AS THE REFERENCE GROUP*/  
DATA FREQ_TABLE2; SET FREQ_TABLE1;  
  IF TRT01PN=3 THEN TRT01PN=0;  
RUN;  
  
/*CALCULATE THE COMMON RISK DIFF FOR EACH COMPLETE DATASET*/  
PROC STDRATE DATA=FREQ_TABLE2  
  METHOD=MH STAT=RISK EFFECT=DIFF;  
  BY _IMPUTATION_;  
  POPULATION GROUP=TRT01PN EVENT=CASE TOTAL=SIZE;  
  STRATA STRATAN / ORDER=DATA STATS(CL=NONE) EFFECT;  
  ODS OUTPUT EFFECT=EFFECT;  
RUN;  
  
/*COMBINING RESULTS USING PROC MIANALYZE*/  
*****  
PROC MIANALYZE DATA=EFFECT;  
  ODS OUTPUT PARAMETERESTIMATES=RISK_DIFF_MH;  
  MODELEFFECTS RiskDiff;  
  STDERR StdErr;  
RUN;
```

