8.3.2 Handling of Missing Data for the Primary Efficacy Endpoint

The NRI-C will be the primary approach for missing data handling in the analyses of the primary efficacy endpoint. The NRI-NC and MI approaches will be used as sensitivity analyses.

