Appendix E. Random Seeds

In case of non-convergence, the random seed will be updated by adding 100000 at each attempt until convergence of model happens. (FSFV: 2019-03-06, 21614; LSFV: 2020-05-05, 22040)

A. Random Seeds for NRI-C

Endpoints	Random Seed	
	MCMC Procedure	PROC MI
All EASI related endpoints	21614	22040
Worst Pruritus NRS improvement ≥ 4	21615	22041

Appendix F. Non-Responder Imputation Incorporating Multiple Imputation to Handle Missing Data Due to COVID-19 Pandemic for Dichotomized Outcome Variables**1.0 Overview****1.1 Background and Justification for Missing at Random (MAR) Assumption**

The COVID-19 pandemic is interfering with the conduct of many ongoing trials, with potential impacts on treatment duration and the collection, analysis and the interpretation of clinical trial data. Some protocol-specified visits in the clinical trials may be impacted due to COVID-19 infection or logistical restrictions during the pandemic. For example, some scheduled visits may be missed due to self-quarantine or local government restrictions on travel; some visits may also be delayed or canceled due to healthcare resource constraints during the pandemic. Impacted visits due to COVID-19 will be recorded in the database. The probability of having missed visits and missing data due to COVID-19 infection or logistical restrictions related to the COVID-19 pandemic can be reasonably assumed to be unrelated to the unobserved values. Therefore, for the purpose of statistical analysis, it is reasonable to assume that these missing data are missing at random (MAR) and the statistical models that require MAR assumption are appropriate. In some cases, sensitivity analyses may be performed to assess the impact of missing data and the robustness of the conclusion.

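### The sample code in SAP Appendix F analyses the dataset without the non-responder override, so the printed NRI-C and MI runs coincide

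*SAP*

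**What the plan says.** **Governing text.** SAP 8.3.2 states: "The NRI-C will be the primary approach for missing data handling in the analyses of the primary efficacy endpoint". SAP 8.3.3 agrees and gives NRI-NC and MI as sensitivity analyses. Under SAP 8.2.1 and Appendix F, 2.1 and 2.4, NRI-C uses multiple imputation only for values missing because of COVID-19. Other missing values, and all visits after rescue, are non-response. The one exception is a subject who responds both before and after the missed window. SAP 8.2.1 also makes post-rescue subjects non-responders in the MI sensitivity analysis, whatever value was imputed.

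**Sample code (SAP Appendix F, 3.0), in printed order.**

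1. Imputed EASI values are dichotomised into a dataset `ALL`.
2. A placeholder reads "DATA HANDLING STEPS TO MERGE COVID-19 STATUS OMITTED".
3. A comment reads "FOR MI, SKIP THE FOLLOWING CODE, PROCEED TO THE CODE AFTER ANALYSIS" (it continues with the word MODEL).
4. The override starts with "DATA ALLF; SET ALL" and includes "IF COVID19_16 NE 'Y' THEN EASI75_16=EASI75NRI_16".
5. Then comes "PROC SORT DATA=ALLF; BY _IMPUTATION_ SUBJID; RUN".
6. The analysis opens with "PROC FREQ DATA=ALL" and passes its counts to PROC STDRATE and PROC MIANALYZE.

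The imputation step uses seed 22040. Appendix E gives that seed for EASI endpoints in its only table, headed "A. Random Seeds for NRI-C".

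**The concern.** The override is what makes NRI-C differ from plain multiple imputation. In the listing it goes into a dataset that no later step uses. Followed as printed, the primary analysis would keep imputed responses for subjects whose data are missing for non-COVID reasons. It would do the same for rescued subjects unless the omitted block deals with them. The MI sensitivity run skips the override block and then reads the same input, so it would reproduce the primary result instead of testing it. NRI-NC would be the only distinct missing-data analysis left.

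This is the only program printed for the primary endpoint, and it takes Week 16 EASI 75 as its example. A programmer or an independent validator may well start from it.

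**Working it through.** **Data flow**

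- Override path: `EASI_MONO` → `EASI_FULL` → `ALL` → `ALLF` → sort. Nothing reads `ALLF` after the sort.
- Analysis path: `ALL` → `COUNT_TABLE` → `FREQ_TABLE` → `FREQ_TABLE1` → `FREQ_TABLE2` → STDRATE → MIANALYZE.

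Building `ALLF` with a SET statement leaves `ALL` unchanged, so the override reaches no estimate. The omitted merge block precedes the creation of `ALLF` and cannot redirect the later step. With one imputation step, one seed and one input, the two printed paths are identical. A different MI seed would separate them only by Monte Carlo error.

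**A second gap**

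Reading `ALLF` is not a complete repair. The override is skipped when the COVID flag is Y. A rescued subject whose Week 16 visit was flagged would keep an imputed response, against SAP 8.2.1, unless the omitted block prevents it.

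**The plan's own figure**

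Inputs from SAP 2.4: 325 per arm, 50% against 62%, two-sided 0.05.

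- SE = sqrt(0.50×0.50/325 + 0.62×0.38/325) = 0.03865, so z at the planned difference = 0.12/0.03865 = 3.10.
- Null SE at the pooled 56% = sqrt(2×0.56×0.44/325) = 0.03894. Power = Φ((0.12 − 1.96×0.03894)/0.03865) = Φ(1.13) = 87.1%, which agrees with the stated power of more than 80%.

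**Size of the error**

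The documents give no missing or rescue rates, so these inputs are assumptions. The share rescued or missing for non-COVID reasons at Week 16 is 6% in one arm and 12% in the other. Imputed response q is 40% to 60%. A fraction r of the affected subjects, equal in both arms, is already settled (rescue set to 0 in the omitted block, or before-and-after responders who are also imputed as responders).

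Shift = (1 − r) × (share_upa × q_upa − share_dup × q_dup), added to planned rates of 50% and 62%. The z is unstratified and ignores between-imputation variance. With q_upa ≥ q_dup:

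| Arm with 12% | r | Shift (points) | z |
|---|---|---|---|
| Dupilumab | 0 | -3.6 to -1.2 | 2.21 to 2.83 |
| Upadacitinib | 0 | +2.4 to +4.8 | 3.78 to 4.45 |
| Dupilumab | 0.5 | -1.8 to -0.6 | 2.66 to 2.97 |
| Upadacitinib | 0.5 | +1.2 to +2.4 | 3.44 to 3.76 |

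- Worked lower end (dupilumab 12%, q = 60% in both arms): 0.50 + 0.12×0.60 = 57.2% against 0.62 + 0.06×0.60 = 65.6%; 0.084/0.03805 = 2.21.
- Equal shares: 0 to +1.2 points at 6% and 0 to +2.4 points at 12%. The shift is zero only if imputed response is also equal.
- If q may differ freely by arm, the shift is 1.2 to 4.8 points in either direction. The extreme against upadacitinib (q 40% there, 60% on dupilumab) gives 57.2% against 64.4%, z = 1.89. It reverses the planned ordering of response, so I give it no weight.

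**A smaller true effect**

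Assume NRI-C rates of 50% and 57%, so z = 0.07/0.03903 = 1.79, with 6% of dupilumab and 12% of upadacitinib subjects affected. The printed code then gives 52.4% against 61.8% (q = 40% in both arms; z = 2.43), rising to 52.4% against 64.2% (q 60% against 40%; z = 3.07).

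**Emulation**

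A simplified emulation used K = 30, Mantel-Haenszel differences, Rubin's rules, 200 replicates and 3% COVID missing. Underlying rates were 50% and 62%, and the before-and-after exception was not modelled. With 5% non-COVID missing and 5% rescued per arm, `ALL` gave a difference of 12.1 points and `ALLF` 11.1. With missing 5% on dupilumab and 10% on upadacitinib, and 5% rescued per arm, they gave 11.9 and 7.7. With both rates at 10% on dupilumab and 5% on upadacitinib, they gave 11.9 and 15.8.

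**The case against.** - **It is only sample code.** The text in SAP 8.2.1 and Appendix F, 2.1 and 2.4 is unambiguous, and the code's own comments describe the override. The listing cannot be run as it stands, because the MCMC step, the COVID flags and the NRI variables are not created in it. Code written from the text would be right, and identical NRI-C and MI outputs would probably be noticed. All of this stands, and it is why this is a correction to the appendix and not a criticism of the method. It does not make the listing right.
- **`ALL` is the correct source for the MI branch.** It is, apart from the rescue rule. The missing piece is any instruction to switch to `ALLF` for NRI-C.
- **The rescue gap may not exist.** Appendix F, 2.4 groups post-rescue visits with missing data from non-COVID causes, so a post-rescue visit might never carry the flag. That is a fair reading. It depends on how the flag is derived, which the listing omits, so the point remains conditional.
- **The size is assumed.** It is, and the 60% cap is somewhat low. Suppose affected subjects were imputed at the response rate of unaffected subjects. With 12% affected on upadacitinib, those rates are 0.50/0.94 = 53.2% and 0.62/0.88 = 70.5%. The shift becomes +5.3 points (z = 4.60), slightly beyond the table. With 12% on dupilumab it is -2.9 points (z = 2.40), inside it.
- **The conflict turns on one letter.** Other lines of the published listing look garbled, so the source program should be checked. A lost letter is possible but not the likeliest explanation.

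**Conclusion.** The concern holds. As printed, the NRI-C and MI paths coincide, and the shared result omits the non-responder rule that defines the primary estimator. It is not necessarily the SAP's MI analysis either, since that also requires non-response after rescue.

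The direction and size depend on rates that the documents do not give. Under the 6%/12% assumptions, starting from the planned 12 points and with imputed response at least as high on upadacitinib, no case takes z below 1.96. With a smaller true difference the error could change the conclusion, as the 50% against 57% example shows.

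This should be fixed. The stated method needs no change.

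A lesser point is leftover placebo wording: the comparison named in Appendix F, 2.5.1, the comment on the reference group, and a recode of treatment code 3 that never fires when the arms are coded 1 and 2. It can affect only the sign or labelling of the difference.

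**What to change.** 1. In the NRI-C branch, read `ALLF` in PROC FREQ and carry it through the later steps. Keep `ALL` for the MI branch, and name the dataset for each branch in the comments.
2. Set post-rescue response to 0 in both branches, whatever the COVID flag, as SAP 8.2.1 requires.
3. Replace the placebo wording in Appendix F, 2.5.1 and in the code comment, and correct the recode so that dupilumab is the reference.
4. State in Appendix F that the SAP text governs where the sample code differs.

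The cost is a few lines of code and one sentence in the appendix.

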Appendix G. Rescue Definition

The topical and systemic medications for AD therapy are coded to the following drug classes. Among these AD medications, the potential AD rescue medications are determined through a medical review process.

3. Plain Topical Corticosteroids
4. High Potency Topical Corticosteroids
5. Medium Potency Topical Corticosteroids
6. Low Potency Topical Corticosteroids
7. Topical Calcineurin Inhibitor Therapy
8. Other Topical therapy (not including moisturizers/emollients)
9. Biologic Systemic Therapy
10. Non-biologic systemic therapy
11. Other Systemic Therapy
12. Phototherapy

Concomitant medications (with the start date after the first date of study drug) that are categorized as "potential AD rescue" per medical review AND in categories 1 – 10 above are considered as rescue medications.

The medical review process is documented in the Rescue Medication Medical Review Process – Upadacitinib AD.

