## Rescue Therapy

Rescue treatment for AD may be provided, if medically necessary at the discretion of the investigator.

Investigators should attempt to limit the first step of rescue therapy to topical medications, and escalate to systemic medications only for those subjects who do not respond adequately after at least 7 days of topical treatment.

Subjects who receive topical rescue treatment during the study treatment period can continue study drug.

If a subject needs rescue treatment with a systemic agent (including but not limited to corticosteroids, cyclosporine, methotrexate [MTX], mycophenolate mofetil, azathioprine) or phototherapy, study drug should be permanently discontinued prior to the initiation of rescue systemic agent or phototherapy.

Subjects who permanently discontinue study drug are encouraged to continue to participate in the study (no study drug given) and complete the schedule of study visits and assessments.

Investigators should conduct efficacy and safety assessments (e.g., disease severity scores, safety labs) before administering any rescue treatment. An unscheduled visit may be used for this purpose if necessary.

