8.2.1 Categorical Endpoints

- The primary approach for handling missing data in the analysis of categorical endpoints (including the primary endpoint) will use Non-Responder Imputation while incorporating Multiple Imputation (MI) to handle missing data due to COVID-19 (NRI-C).

The NRI-C will categorize any subject who does not have an evaluation during a pre-specified visit window (either due to missing assessment or due to early withdrawal from the study) as a non-responder for the visit. The only exceptions are: 1) when the subject is a responder both before and after the visit window, the subject will be categorized as a responder for the visit. 2) missing data due to COVID-19 infection or logistical restriction will be handled by Multiple Imputation. In addition, all assessments after the start of rescue medications will not be included in the analyses; as a result, subjects will be counted as non-responders thereafter and will not be imputed by MI. NRI-C will not be applied to the endpoint of improvement of daily Worst Pruritus NRS ≥ 4 up to Day 28.

- A sensitivity analysis for categorical endpoints will use NRI with No special data handling for missing due to COVID-19 (NRI-NC).

NRI-NC will be performed in the same way as NRI-C without the exception #2 above. That is, missing due to COVID-19 infection or logistical restriction will also be counted as non-responders.

Subjects whose change/percent change from Baseline cannot be calculated because of a missing Baseline will be considered as a non-responder at all post-baseline visits in both NRI-C and NRI-NC approaches. NRI-NC will be primary approach for the efficacy endpoint of improvement of daily Worst Pruritus NRS ≥ 4 up to Day 28.

- Multiple Imputation (MI), a sensitivity analysis for the primary endpoint and key secondary categorical endpoints: Markov Chain Monte Carlo (MCMC) will be first applied to augment data into monotonic missing pattern and PROC MI will be used to generate 30 datasets using the regression method. The variables to be included in the imputation model are: treatment group, stratum (vIGA-AD categories), gender, Baseline, and measurements at each visit up to the end of the analysis period. The random seed for MCMC and the random

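### SAP Appendix G labels its ten drug classes 3 to 12 but defines rescue by categories 1 to 10, so the printed rule leaves out Other Systemic Therapy and Phototherapy; labels and range must be made to agree.

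*SAP*

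**What the plan says.** SAP Appendix G sorts topical and systemic medications for atopic dermatitis into ten drug classes. The first is printed as "3. Plain Topical Corticosteroids". The last three are "10. Non-biologic systemic therapy", "11. Other Systemic Therapy" and "12. Phototherapy". A concomitant medication started after the first study drug date is rescue if it meets two conditions: medical review has categorised it as potential rescue, "AND in categories 1 – 10 above are considered as rescue medications".

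SAP Section 8.2.1 sets the consequence for categorical endpoints, including the primary: "all assessments after the start of rescue medications will not be included in the analyses; as a result, subjects will be counted as non-responders thereafter". Section 8.2.2 drops measurements after rescue from the MMRM.

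Protocol Section 5.4 (Rescue Therapy) places systemic agents and phototherapy among the rescue treatments: when either is needed, "study drug should be permanently discontinued prior to the initiation of rescue systemic agent or phototherapy". It also encourages subjects who stop study drug to stay in the study and complete the visits.

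**The concern.** The range in the rule does not match the labels it points to. A programmer who codes the range against the printed labels would never set the rescue flag for classes 11 and 12. Medical review could not correct this, because both conditions must be met: a reviewer may flag phototherapy as rescue, and it still fails the category test.

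The definition matters because it triggers non-response for EASI 75 at Week 16 and for the ranked responder endpoints, and it removes data from the MMRM for the ranked pruritus endpoints. The NRI-NC and MI sensitivity analyses use the same trigger, so they would repeat a misclassification and could not reveal it. SAP Section 8.2 has no separate rule that makes a subject a non-responder for stopping study drug. Because visits continue after study drug stops, a Week 16 EASI can be observed after phototherapy. Under the printed rule, a 75% reduction reached that way would count as a response for the randomised arm.

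**Working it through.** **Step 1. Labels against range (SAP Appendix G).**

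- Printed labels: 3 to 12, so 12 − 3 + 1 = 10 classes.
- Range in the rule: 1 to 10, so 10 − 1 + 1 = 10 categories.
- Overlap: 3 to 10, so 10 − 3 + 1 = 8 classes in range.
- Out of range: 11 and 12, so 2 classes.
- Numbers in the rule with no class: 1 and 2.

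The two counts are equal (10 and 10) and the labels are displaced by two. If the list is renumbered 1 to 10, all ten classes are in range.

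**Step 2. Who could be misclassified for EASI 75 at Week 16.** A subject must meet all of these:

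1. received a therapy coded to printed class 11 or 12 before the Week 16 assessment;
2. had no earlier rescue coded to classes 3 to 10, since that alone makes the subject a non-responder from then on (SAP 8.2.1);
3. had an observed EASI 75 response at Week 16. The responder-before-and-after rule and the COVID-19 imputation could in principle supply a response for a missing visit, but these are narrow cases.

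**Step 3. Size per subject.** With 325 per arm (SAP 2.4), one misclassified subject changes that arm's rate by 1/325 = 0.00308, or 0.31 percentage points.

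**Step 4. Illustration on the difference.** The documents give no rate of use for these classes, so the shares below are assumptions. The planning values come from SAP 2.4: 50% on dupilumab, a 12-point difference, 325 per arm, two-sided 0.05.

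Power = Φ{[δ − 1.96·√(2p̄(1 − p̄)/n)] / √[(p₁(1 − p₁) + p₂(1 − p₂))/n]}

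Plan's own case (50% against 62%): p̄ = 0.56, √(2 × 0.56 × 0.44/325) = 0.03894, and √[(0.2500 + 0.2356)/325] = 0.03865. So Φ[(0.12 − 0.0763)/0.03865] = Φ(1.13) = 87.1%, which agrees with the SAP's claim of more than 80%.

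| Assumed share of arm wrongly counted as responders | Expected difference | Power |
|---|---|---|
| None | 12.0 points | 87.1% |
| 0.5% dupilumab only (about 2 subjects) | 11.5 points | 84.2% |
| 1% dupilumab only (about 3 subjects) | 11.0 points | 80.9% |
| 2% dupilumab only (about 7 subjects) | 10.0 points | 73.2% |
| 1% in each arm | 12.0 points | 87.2% |
| 1% upadacitinib only | 13.0 points | 91.8% |

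The table shows that the sign depends entirely on which arm is affected. It does not estimate what will happen.

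**The case against.** The strongest reply is that this is a labelling slip and nothing more. The list has ten items and the rule names ten categories. The literal reading needs categories 1 and 2, which do not exist. Reading the rule as covering all ten classes is coherent and agrees with Protocol 5.4. Numbering is also irregular nearby: the reference list of SAP Appendix F has two entries numbered 1. The labels may even have been shifted when the PDF was read. In addition, the SAP says that medications are coded to named classes and reviewed under a separate process document, and nothing shows that programming uses the printed numbers.

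The reach is narrow even on the literal reading. Biologic and non-biologic systemic therapy (9 and 10) remain in range. Methotrexate, cyclosporine, azathioprine, mycophenolate and corticosteroids appear in Protocol 5.3 under the non-biologic systemic heading, so they probably code to class 10, although the SAP gives no drug-level mapping. Protocol 5.4 also asks investigators to try topical rescue first, and subjects given in-range topical rescue are already non-responders.

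Most of this stands. A reader might infer that the sponsor chose not to treat phototherapy as rescue, or that the treatment difference will shift by one to two points. The documents support neither. The matching count of ten and Protocol 5.4 point away from intent. A shift of that size needs an assumed 1% to 2% usage confined to one arm, with every such subject responding. What does not fall away is that the current text gives an operative range that disagrees with its own list, and probable intent is not a specification.

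**Conclusion.** The mismatch is in the current text of SAP Appendix G. Followed as printed, the rule omits two of ten classes and conflicts with Protocol 5.4. The likely intent is that all ten classes count, so this is a specification error to correct, not evidence of a deliberate exclusion or of a biased primary analysis.

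Its certain size is 0.31 percentage points of one arm's EASI 75 rate per misclassified subject. How many subjects are affected, and in which arm, cannot be derived from the documents. If use were equal in both arms, the difference would be about unchanged. The effect on the MMRM endpoints cannot be sized either.

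The conclusion assumes that the labels 3 to 12 also stand in the source file. If the source reads 1 to 10, the point lapses. It is worth settling because the definition drives the primary endpoint and the correction has no drawback.

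**What to change.** 1. Check the class labels in the source file of SAP Appendix G.
2. If they read 3 to 12, either renumber the list 1 to 10 or replace the numeric range with wording such as *any of the ten categories listed above*. The second option does not depend on list numbering.
3. Reconcile the result with Protocol Section 5.4, so that the SAP's analysis definition and the protocol's description of rescue cover the same therapies.
4. Confirm before unblinding that the rescue program and the medical review process document use all ten classes.

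The cost is one SAP line and a short programming check. No data collection or sample size changes.
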